#### 5.1.19 Patient Reported Outcomes (PROs)

Quality of Life (QOL) assessments will be performed at baseline, end of treatment, and at 3, 6, 12, and 24 months after completion of treatment. If an additional tumor assessment is done prior to 3 years from study entry, one final QOL assessment is requested. Please refer to Appendix V for the complete schedule.

QOL will continue to be collected for all patients post recurrence.

Paper questionnaires will be completed by the patient, and then data from the questionnaire should be entered into Medidata Rave within 7 days of completion. The original copy needs to be kept in the study subject's research binder. Refer to the ECOG website for a copy of the questionnaire.

Rev. 6/14

### 5.2 Adverse Event Reporting Requirements

#### 5.2.1 Purpose

Adverse event (AE) data collection and reporting, which are required as part of every clinical trial, are done to ensure the safety of the patients enrolled, as well as those who will enroll in future studies using similar agents.

- **Routine reporting:** Adverse events are reported in a routine manner at scheduled times during a trial using Medidata Rave.
- **Expedited reporting:** In addition to routine reporting, certain adverse events must be reported in an expedited manner for timelier monitoring of patient safety and care. The following sections provide information and instructions regarding expedited adverse event reporting.

#### 5.2.2 Terminology

- **Adverse Event (AE):** Any untoward medical occurrence associated with the use of a drug in humans, whether or not considered drug related. Therefore, an AE can be **ANY** unfavorable and unintended sign (including an abnormal laboratory finding), symptom, or disease temporally associated with the use of a medicinal product, whether or not considered related to the medicinal product.

- **Attribution:** An assessment of the relationship between the adverse event and the protocol treatment, using the following categories.

ATTRIBUTION	DESCRIPTION
Unrelated	The AE is clearly NOT related to treatment
Unlikely	The AE is doubtfully related to treatment
Possible	The AE may be related to treatment
Probable	The AE is likely related to treatment
Definite	The AE is clearly related to treatment

- **CTCAE:** The NCI Common Terminology Criteria for Adverse Events provides a descriptive terminology that is to be utilized for AE reporting. A grade (severity) is provided for each AE term.
- **Expectedness:** Any adverse event, the type or severity of which is consistent with the current investigator’s brochure, product label, and/or the protocol document

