#### 5.2.4 Determination of reporting requirements

[figure not shown]
Many factors determine the reporting requirements of each individual protocol, and which events are reportable in an expeditious manner, including:

- the phase (0, 1, 2, or 3) of the trial
- whether the patient has received an investigational or commercial agent or both
- the Common Terminology Criteria for Adverse Events (CTCAE) grade
- the relationship to the study treatment (attribution)
- the expectedness of the adverse event

**Using these factors, the instructions and tables in the following sections have been customized for protocol E3311 and outline the specific expedited adverse event reporting requirements for study E3311.**

Rev. Add8

5.2.5 Steps to determine if an event is to be reported in an expedited manner

5.2.6 Expedited Reporting Requirements for Arms S, A, B, C and D on protocol E3311

Commercial Agents: Cisplatin, Carboplatin

Expedited reporting requirements for adverse events experienced by patients on arm(s) with commercial agents only					
Attribution	Grade 4		Grade 5 a		ECOG-ACRIN and Protocol-Specific Requirements
	Unexpected	Expected	Unexpected	Expected	
Unrelated or Unlikely			7 calendar days	7 calendar days	See footnote (b) for special requirements.
Possible, Probable, Definite	7 calendar days		7 calendar days	7 calendar days	
7 Calendar Days: Indicates a full CTEP-AERS report is to be submitted within 7 calendar days of learning of the event.					

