
a This includes all deaths within 30 days of the last dose of treatment regardless of attribution. NOTE: Any death that occurs > 30 days after the last dose of treatment and is attributed possibly, probably, or definitely to the treatment must be reported within 7 calendar days of learning of the event.
 
b Protocol-specific expedited reporting requirements: The adverse events listed below also require expedited reporting for this trial:
 
Serious Events: Any event following treatment that results in persistent or significant disabilities/incapacities, congenital anomalies, or birth defects must be reported via CTEP-AERS within 7 calendar days of learning of the event. For instructions on how to specifically report these events via CTEP-AERS, please contact the AEMD Help Desk at [contact] or [contact]. This will need to be discussed on a case-by-case basis.
 
Bleeding: Any grade 3-4 bleeding (requiring hemostasis in the operating room), regardless of attribution or expectedness, must be reported via CTEP-AERS within 7 calendar days of learning of the event.
					

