8.1.11 Side Effects

1. Renal: A dose-related, cumulative renal tubular injury can occur; adequate hydration and diuresis usually minimize the risk. Salt-wasting nephropathy and/or orthostatic hypotension with hyporeninemic hypoaldosteronism can occur in up to 10% of patients.
2. Neurologic: A dose-related ototoxicity, manifested by high-frequency hearing loss and tinnitus, occurs in about 30% of patients. Paresthesias, decreased vibratory, position, and touch sensations are less common; particularly at cumulative doses <400 mg/m^2.
3. Hematologic: Mild leukopenia and thrombocytopenia occur in 25-30% of patients, but are rarely dose-limiting; anemia is less common. A potentially fatal hemolytic uremic syndrome has been reported.
4. Gastrointestinal: Severe, dose-limiting nausea and vomiting occur in almost 100% of patients unless adequate antiemetic prophylaxis is given. Even with successful prophylaxis of acute nausea a delayed (72-96 hour) reaction, requiring additional therapy may occur. Anorexia and taste changes may also occur.
5. Hypersensitivity: Allergic reactions are reported in up to 20% of patients Symptoms include: rash, facial edema, wheezing, hypotension, and tachycardia. Severe anaphylaxis is rare.
6. Other: Electrolyte wasting (magnesium, potassium and sodium), papilledema, optic neuritis, retrobulbar neuritis are reported.

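### Section 5.2.2 lets a match on type or severity make an event expected, so read literally greater severity alone never puts a related grade 4 event of a listed type into 7-day reporting

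*Combined protocol and SAP*

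**What the plan says.** The protocol's terminology section (5.2.2) describes an expected event as "Any adverse event, the type or severity of which is consistent with the current" investigator's brochure, product label and/or protocol document. The same section ties severity to the CTCAE grade: "A grade (severity) is provided for each AE term". The visible text does not define an unexpected event separately.

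Section 5.2.4 lists "the expectedness of the adverse event" among the factors that determine reporting, separately from grade and attribution. In the 5.2.6 table, which covers Arms S, A, B, C and D, the row "Possible, Probable, Definite" has a 7-calendar-day entry for grade 4 unexpected events and a blank for grade 4 expected events. The entry is explained as "Indicates a full CTEP-AERS report is to be submitted within 7 calendar days of learning of the event". Grade 5 events carry the 7-day entry whether expected or not.

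Three rules apply regardless of expectedness:

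- **Bleeding (5.2.6, footnote b):** "Any grade 3-4 bleeding (requiring hemostasis in the operating room), regardless of attribution or expectedness, must be reported via CTEP-AERS within 7 calendar days".
- **Disability and birth defects (5.2.6, footnote b):** "Any event following treatment that results in" persistent or significant disability or incapacity, a congenital anomaly or a birth defect.
- **Secondary malignancy (5.2.8):** a cancer caused by treatment needs both routine and expedited reporting.

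**The concern.** Naming severity in a definition of expectedness should allow a reaction worse than described to be treated as new information. The disjunctive wording prevents that: once the type is listed, the severity test no longer matters. Section 5.2.1 says that expedited reporting exists so that patient safety can be followed in a more timely way than routine reporting allows. A related grade 4 reaction well beyond its documented severity is the kind of signal that purpose covers, and the literal definition removes it from the 7-day route. At stake is the speed at which such events are reported. Whether they are recorded at all is not in question.

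**Working it through.** No sample size, power or event count is involved, so the check is logical.

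**Inputs.** The definition comes from 5.2.2. The grade 4 entries for related events come from the 5.2.6 table. The overriding rules come from 5.2.6 footnote b and from 5.2.8.

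**Step 1: the literal rule and its complement.** Let T mean that the type is consistent with the reference document, and S that the severity is.

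- As written: expected = T or S, so unexpected = (not T) and (not S).
- With both required: expected = T and S, so unexpected = (not T) or (not S).

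**Step 2: carry each combination into the related grade 4 row.**

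| Type consistent | Severity consistent | As written | If both are required |
|---|---|---|---|
| Yes | Yes | Expected, no 7-day report | Expected, no 7-day report |
| Yes | No | Expected, no 7-day report | Unexpected, 7-day report |
| No | Yes | Expected, no 7-day report | Unexpected, 7-day report |
| No | No | Unexpected, 7-day report | Unexpected, 7-day report |

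As written, one of the four combinations leads to a 7-day report; with both required, three do. These are counts of logical cases, not proportions of events. The second row carries the practical weight. The third is a literal consequence that few sites would apply, because severity has little meaning for a type the document does not list.

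**Step 3: apply the exceptions.** The bleeding, disability or birth-defect, and secondary-malignancy rules recover some events in rows two and three. Nothing visible recovers the rest.

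**Step 4: an illustration.** Section 8.1.11 says of cisplatin: "Mild leukopenia and thrombocytopenia occur in 25-30% of patients, but are rarely dose-limiting". Measured against that sentence alone, a related grade 4 thrombocytopenia is of a listed type and exceeds the listed severity. It is expected as written and unexpected if both attributes must match. Two things limit the example. The product label also counts as a reference and is not in the documents. The cisplatin dose-modification table in 5.3.2.1 already provides for low counts, neutropenic fever and stopping chemotherapy, so a site could call the event expected under either rule.

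**The case against.** The strongest objection is that 5.2.2 may not be what sites follow. The heading of 5.2.5 announces the steps for deciding on expedited reporting, but its content is not visible in the text available for review, and 5.2.3 refers sites to external CTEP-AERS guidelines. Either could state how expectedness is judged. This limits any claim about what sites do. It does not repair 5.2.2: a different rule in 5.2.5 would be a conflict to reconcile.

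A second objection is that no passage says both attributes must match, so the wording might be called merely loose. It is true that the intended rule is not stated. The case rests on internal logic: under the literal rule severity can never make a listed type unexpected, which sits badly with the purpose given in 5.2.1.

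Third, the practical effect may be small. Many cisplatin effects in 8.1.11 carry no severity descriptor, and others are already described as severe or potentially fatal. For carboplatin, 8.2.12 calls thrombocytopenia dose limiting. For such effects the two rules may often agree. This stands, and it is why no event count is offered.

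A reader might also infer that the grade 4 unexpected cell is left nearly empty, or that affected events stay unseen for about six months because the DSMC meets twice a year (9.9). The documents support neither. Events matching on neither attribute still fall in the cell, and on any ordinary reading so do events of an unlisted type. Affected events are still entered in Rave at the scheduled times (5.2.1), and nothing says that they wait there for a DSMC meeting.

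**Conclusion.** The point holds as a flaw in an operative definition. Under the literal wording of 5.2.2, a possibly, probably or definitely related grade 4 event of a listed type cannot become unexpected through greater severity. Unless an exception applies, it therefore receives routine Rave reporting only. Grade 5 events are unaffected.

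The size is not known. Section 9.3 expects about 120 high-risk patients, the group treated with cisplatin on Arm D; that is an arm size and not a count of affected events. It would be wrong to conclude that any particular reaction, such as grade 4 thrombocytopenia, is certain to escape, because that depends on a product label that is not in the documents.

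The conclusion assumes that sites read the definition as written and that the 5.2.5 steps do not impose a different rule. It concerns the timeliness of safety reporting and affects no endpoint or analysis. A correction is worthwhile because it is small and specific.

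**What to change.** 1. In 5.2.2, state that an event is expected only if both its type and its severity are consistent with the reference document, and unexpected if either is not.
2. Replace the and/or list with the reference document that governs for commercial cisplatin and for commercial carboplatin. Otherwise a site can still choose the source that makes an event expected.
3. Check the 5.2.5 steps against the new wording and align them if they differ.

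The 5.2.6 table and its exceptions can stay as they are. The cost is a short protocol amendment and some additional expedited reports, mainly from Arm D.

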### 5.2.3 Reporting procedure

This study requires that expedited adverse event reporting use CTEP’s Adverse Event Reporting System (CTEP-AERS). CTEP’s guidelines for CTEP-AERS can be found at <http://ctep.cancer.gov>. A CTEP-AERS report must be submitted electronically to ECOG-ACRIN and the appropriate regulatory agencies via the CTEP-AERS Web-based application located at <http://ctep.cancer.gov>.

In the rare event when Internet connectivity is disrupted a 24-hour notification is to be made by telephone to

- the AE Team at ECOG-ACRIN [contact])
- the FDA ([name])

An electronic report **MUST** be submitted immediately upon re-establishment of internet connection.

**Supporting and follow up data:** Any supporting or follow up documentation must be uploaded to the Supplemental Data Folder in Medidata Rave within 48-72 hours. In addition, supporting or follow up documentation must be faxed to the FDA [contact]) in the same timeframe.

**NCI Technical Help Desk:** For any technical questions or system problems regarding the use of the CTEP-AERS application, please contact the NCI Technical Help Desk at [[contact]](mailto:[contact]) or by phone at [name].

#### 5.2.4 Determination of reporting requirements

[figure not shown]
Many factors determine the reporting requirements of each individual protocol, and which events are reportable in an expeditious manner, including:

- the phase (0, 1, 2, or 3) of the trial
- whether the patient has received an investigational or commercial agent or both
- the Common Terminology Criteria for Adverse Events (CTCAE) grade
- the relationship to the study treatment (attribution)
- the expectedness of the adverse event

**Using these factors, the instructions and tables in the following sections have been customized for protocol E3311 and outline the specific expedited adverse event reporting requirements for study E3311.**

Rev. Add8

5.2.5 Steps to determine if an event is to be reported in an expedited manner

5.2.6 Expedited Reporting Requirements for Arms S, A, B, C and D on protocol E3311

Commercial Agents: Cisplatin, Carboplatin

Expedited reporting requirements for adverse events experienced by patients on arm(s) with commercial agents only					
Attribution	Grade 4		Grade 5 a		ECOG-ACRIN and Protocol-Specific Requirements
	Unexpected	Expected	Unexpected	Expected	
Unrelated or Unlikely			7 calendar days	7 calendar days	See footnote (b) for special requirements.
Possible, Probable, Definite	7 calendar days		7 calendar days	7 calendar days	
7 Calendar Days: Indicates a full CTEP-AERS report is to be submitted within 7 calendar days of learning of the event.					

a This includes all deaths within 30 days of the last dose of treatment regardless of attribution. NOTE: Any death that occurs > 30 days after the last dose of treatment and is attributed possibly, probably, or definitely to the treatment must be reported within 7 calendar days of learning of the event.
 
b Protocol-specific expedited reporting requirements: The adverse events listed below also require expedited reporting for this trial:
 
Serious Events: Any event following treatment that results in persistent or significant disabilities/incapacities, congenital anomalies, or birth defects must be reported via CTEP-AERS within 7 calendar days of learning of the event. For instructions on how to specifically report these events via CTEP-AERS, please contact the AEMD Help Desk at [contact] or [contact]. This will need to be discussed on a case-by-case basis.
 
Bleeding: Any grade 3-4 bleeding (requiring hemostasis in the operating room), regardless of attribution or expectedness, must be reported via CTEP-AERS within 7 calendar days of learning of the event.
					

5.2.7 Other recipients of adverse event reports and supplemental data

Adverse events determined to be reportable via CTEP-AERS must also be reported by the institution, according to the local policy and procedures, to the Institutional Review Board responsible for oversight of the patient.

5.2.8 Second Primary Cancer Reporting Requirements

All cases of second primary cancers, including acute myeloid leukemia (AML) and myelodysplastic syndrome (MDS), that occur following treatment on NCI-sponsored trials must be reported to ECOG-ACRIN using Medidata Rave

- **A second malignancy is a cancer that is UNRELATED to any prior anti-cancer treatment (including the treatment on this protocol). Second malignancies require ONLY routine reporting as follows:**

1. Complete a Second Primary Form in Medidata Rave in 14 days.
  2. Upload a copy of the pathology report to ECOG-ACRIN via Medidata Rave confirming the diagnosis.
  3. If the patient has been diagnosed with AML/MDS, upload a copy of the cytogenetics report (if available) to ECOG-ACRIN via Medidata Rave.
- **A secondary malignancy is a cancer CAUSED BY any prior anti-cancer treatment (including the treatment on this protocol). Secondary malignancies require both routine and expedited reporting as follows:**
    1. Complete a Second Primary Form in Medidata Rave in 14 days.
    2. Report the diagnosis via CTEP-AERS at <http://ctep.cancer.gov>
      - *Report under a.) leukemia secondary to oncology chemotherapy, b.) myelodysplastic syndrome, or c.) treatment related secondary malignancy*
    3. Upload a copy of the pathology report to ECOG-ACRIN via Medidata Rave and submit a copy to NCI/CTEP confirming the diagnosis.
    4. If the patient has been diagnosed with AML/MDS, upload a copy of the cytogenetics report (if available) to ECOG-ACRIN via Medidata Rave and submit a copy to NCI/CTEP.

**NOTE:** The Second Primary Form and the CTEP-AERS report should not be used to report recurrence or development of metastatic disease.

**NOTE:** If a patient has been enrolled in more than one NCI-sponsored study, the Second Primary Form must be submitted for the most recent trial. ECOG-ACRIN must be provided with a copy of the form and the associated pathology report and cytogenetics report (if available) even if ECOG-ACRIN was not the patient's most recent trial.

**NOTE:** Once data regarding survival and remission status are no longer required by the protocol, no follow-up data should be submitted via CTEP-AERS or by the Second Primary Form

### 5.3 Dose Modifications

**All toxicity grades below are described using the NCI Common Terminology Criteria for Adverse Events (CTCAE) version 4.0.**

**All appropriate treatment areas should have access to a copy of the CTCAE version 4.0. A copy of the CTCAE version 4.0 can be downloaded from the CTEP website (<http://ctep.cancer.gov>).**

- 5.3.1 The use of colony stimulating factors (G-CSF, GM-CSF), and amifostine are explicitly discouraged. Erythropoietin stimulating agents, such as erythropoietin, and darbepoietin, are prohibited.

Rev. 6/14

5.3.2 Cisplatin

5.3.2.1 Hematologic

Cisplatin will not be given until the ANC  $\geq 1000/\text{mm}^3$  and the platelet count  $\geq 75,000/\text{mm}^3$ . Complete blood count, differential and platelets will be checked weekly during therapy. Dose modifications are as per table below:

Toxicity	Cisplatin Modification
ANC $< 1000/\text{mm}^3$ or Platelets $< 75,000/\text{mm}^3$	Hold therapy 1 week, and treat at full dose if ANC $\geq 1000$ and platelets $\geq 75,000$ If ANC and/or platelets have not recovered after 7 days, lower cisplatin to 30 mg/m  weekly and re-initiate therapy once ANC $\geq 1000$ and platelets $\geq 75,000$ If after dose reduction, ANC $< 1000$ and/or platelets $< 75,000$ on the next day of treatment, hold cisplatin until ANC $\geq 1000$ and platelets $\geq 75,000$ and restart at 20mg/m  . If on the subsequent treatment day, ANC $< 1000$ and/or platelets $< 75,000$ , discontinue further chemotherapy
Neutropenic fever	Hold cisplatin until ANC $\geq 1000$ , and re-start at 30mg/m  . If cisplatin is already at 30mg/m  , restart cisplatin at 20mg/m  . If cisplatin was given at 20mg/m  , discontinue further chemotherapy.

**NOTE:** No dose re-escalations will be allowed.

5.3.2.2 Renal

Cisplatin will not be given if the serum creatinine is  $> 1.6$  mg/dl. Serum creatinine is required before each dose of cisplatin. Modify the cisplatin dose using the following parameters for calculated creatinine clearance determined in the well-hydrated patient using the modified Cockcroft-Gault formula:

$$\{ (140 - \text{age}) (\text{Wt in kg})^* \} / 72 (\text{serum creat mg/dL})$$

\* Wt is actual body weight. With provision to multiply by 0.85 in women.

Calculated Cr clearance	Chemotherapy dose
$> 60$ ml/min	100% (40 mg/m  )
40-60 ml/min	30mg/m 
$< 40$ ml/min	Hold cisplatin

5.3.2.3 Neurotoxicity

Significant (grade 3) myopathy, weakness, or neuropathy; seizure or paralysis should prompt discontinuation of cisplatin. Carboplatin at an AUC of 2 weekly may be substituted under these circumstances.

For grade 2 neurotoxicity hold cisplatin until toxicity improves to  $\leq$  grade 1, then reduce all subsequent doses of cisplatin to 30mg/m^2.

Rev. 2/15

5.3.2.4 Ototoxicity: For clinical hearing loss not requiring a hearing aid or for tinnitus that interferes with activities of daily living but that resolves prior to the next scheduled dose of cisplatin, consider obtaining an audiogram and reduction of cisplatin to 30 mg/m^2 if there is evidence of significant hearing loss. If tinnitus persists on the day of treatment, or if it recurs despite this dose reduction, or for if there is new hearing loss requiring a hearing aid, discontinue cisplatin and switch to carboplatin.

Grade 3 hearing loss in the speech frequency range is an indication to discontinue cisplatin and switch to carboplatin.

5.3.2.5 Other non-hematologic toxicities: For any grade 3 or 4 toxicities not mentioned above and excluding alopecia, nausea, dehydration and mucositis, treatment with cisplatin should be delayed until < grade 2. For grade 1 or 2 toxicities no delays will occur. If cisplatin is held > 2 weeks, it will be permanently discontinued. For grade 4 toxicity requiring hospitalization, cisplatin may be interrupted at the discretion of the treating physician.

